#### **Latent TB**

Any latent TB infection will be reported as an AE and graded appropriately as described in this protocol. No specific listing will be provided for Latent TB infection.

#### **Active TB or NTM infection**

Study participants who develop active TB or NTM infection during the study (conversion demonstrated by IGRA) will be withdrawn from the study. The study participant will be immediately and permanently discontinued from the IMP. The study participant should complete the assessments outlined for the EOT/EW Visit and encouraged to enter the 5-week SFU Period.

Confirmed active TB is always considered an SAE and will be reported in AE section.

#### **5.6.9.5 Potential Drug-Induced Liver Injury (pDILI)**

The number and percentage of participants who meet one or more of the following pDILI criteria at any visit (including unscheduled visits) will be summarized by treatment period and treatment group, based on the SS-r:

- Participants with at least one post-Baseline liver laboratory assessment
- Incidence of potential hepatotoxicity with symptoms potentially associated with hepatitis or hypersensitivity
- Incidence of potential hepatotoxicity with no symptoms potentially associated with hepatitis or hypersensitivity
- Laboratory criteria for pDILI:
  - (AST or ALT  $\geq 3 \times$  ULN) and TBL  $\geq 1.5 \times$  ULN
  - (AST or ALT  $\geq 3 \times$  ULN) and TBL  $\geq 2 \times$  ULN
  - (AST or ALT  $\geq 3 \times$  ULN) and TBL  $\geq 2 \times$  ULN and ALP  $< 2 \times$  ULN (Hy's Law)

In order to meet the above criteria, a study participant must experience the elevation in bilirubin and ALT or AST (and the absence of the ALP elevation) at the same visit. For example, a study participant who experiences a  $\geq 2 \times$  ULN elevation of bilirubin at one visit and a  $\geq 3 \times$  ULN elevation in ALT (or AST) at a subsequent visit has not fulfilled the Hy's law criteria. If participant meets part of one criterion but at least one parameter is unknown, then he/she should not be considered for meeting the criterion.

Additional analyses for liver function tests (LFTs) will be performed to assess the potential for liver toxicities in accordance with the United States Food and Drug Administration guidelines. Per guidelines, the following criteria will be used to define levels of LFT elevation:

- Aspartate aminotransferase (AST):  $> 3 \times$  ULN,  $> 5 \times$  ULN,  $> 8 \times$  ULN,  $> 10 \times$  ULN,  $> 20 \times$  ULN
- Alanine aminotransferase (ALT):  $> 3 \times$  ULN,  $> 5 \times$  ULN,  $> 8 \times$  ULN,  $> 10 \times$  ULN,  $> 20 \times$  ULN
- AST or ALT:  $> 3 \times$  ULN,  $> 5 \times$  ULN,  $> 8 \times$  ULN,  $> 10 \times$  ULN,  $> 20 \times$  ULN
- Total bilirubin (TBL):  $> 1.5 \times$  ULN,  $> 2 \times$  ULN
- Alkaline phosphatase (ALP):  $> 1.5 \times$  ULN

The number and percentage of study participants who meet one or more of the above LFT elevation criteria at any visit (including unscheduled visits) will be summarized by treatment period and treatment group, based on the SS-r.

A listing of results obtained for all scheduled and unscheduled visits will also be provided for study participants who meet at least one of the following criteria:

- (ALT or AST $\geq$ 3xULN) and (TBL  $\geq$  1.5 x ULN)
- (ALT or AST $\geq$ 3xULN) and (TBL  $\geq$  2 x ULN) and (ALP  $<$  2 x ULN)

The listing will show the new ratio, nR, calculated as the ratio of either ALT or AST (whichever is higher) to ALP, expressed as multiples of their ULN, ie, Max (ALT x ULN or AST x ULN)/ ALP x ULN.

## 5.7 Immunogenicity

The immunogenicity analysis will be summarized based on the SS-r by treatment sequence or by visit when applicable. Samples from study participants on placebo will not be tested for anti-drug antibodies (ADA). Consequently, participants randomized to Sequence 3 will be excluded from the analyses described in this section and will not be included in TFLs.

Anti-drug antibodies will be measured using a three-tiered assay approach: screening, confirmatory and titration assay. Any sample confirmed positive for ADA will be assayed to determine whether there is neutralizing potential.

Samples will first be evaluated in the screening assay (reported as 'negative screen' or 'positive screen'), followed by analysis of screened positive samples in the confirmatory assay to confirm the true positivity of the samples (reported as 'negative immuno-depletion' or 'positive immuno-depletion'). Samples that are confirmed as positive in the confirmatory assay will be evaluated in a titration assay to quantify the ADA level and will be reported as titer (reciprocal dilution factor including minimum required dilution (MRD)).

The ADA sample status will be determined for each pre-treatment (Baseline) and post-treatment (post-Baseline) visit where samples were taken for ADA analysis (both scheduled and any unscheduled visits):

**Table 5-6: ADA Sample Status**

ADA sample status	Definition
ADA negative (ADA-)	Sample values that are either 'negative screen' or 'positive screen' and 'negative immuno-depletion' if corresponding rozanolixizumab concentrations are equal or below the validated drug tolerance limit of the ADA assay (200ug/ml rozanolixizumab) allowing detection of 100 ng/ml ADA. Note that if an ADA sample does not have a corresponding PK sample (at the same visit), then it is assumed that the drug concentration is below the drug tolerance limit.
ADA positive (ADA+)	Sample values that are 'positive screen' and 'positive immuno-depletion'
ADA inconclusive	Sample values that are either 'negative screen' or 'positive screen' and 'negative immuno-depletion' but with corresponding rozanolixizumab concentrations above the validated drug tolerance limit of the ADA assay (200ug/ml rozanolixizumab) allowing detection of 100 ng/ml ADA.

ADA sample status	Definition
	Note that if an ADA sample does not have a corresponding PK sample (at the same visit), then it is assumed that the drug concentration is below the drug tolerance limit and therefore this sample cannot be classified as 'Inconclusive'.
Missing	Samples that were collected per schedule but could not be tested for ADA status due to inadequate sample volume, mishandling, or errors in sample collection, processing, storage, etc.
Evaluatable ADA sample	A sample for which the sample status is not missing nor ADA inconclusive

Neutralizing antibody (NAb) sample status (positive/negative/inconclusive/missing) will be determined for ADA positive samples. Samples that are NAb positive will be evaluated in a titration assay to quantify the NAb level and will be reported as titer.

#### Definition of ADA Baseline

The Baseline values for ADA will be based on the last measurement prior to receiving the first dose of rozanolixizumab. For participants randomized to Sequence 1, Baseline is the Visit 3 (Week 1) pre-dose assessment, or Visit 1 (Week -1), if missing. For participants randomized to Sequence 2, Baseline is the Visit 15 (Week 13) pre-dose assessment, or Week 3 (Visit 1), if missing.

#### ADA/NAb Participant Status

The ADA/NAb participant status will be further classified on study participant level as outlined below (Shankar et al. 2014; Rup et al. 2015, Presentation Immunogenicity Summit, 2021, Joleen White, Enabling Clinical Immunogenicity Impact Assessment with Standardized Data Tabulation Models).

The by-participant classifications for ADA status will be derived 3 times:

- For the entire study duration (ie, including all samples from Treatment Periods 1 and 2, and SFU). Note that participants in Sequence 2 will not have samples from Treatment Period 1.
- Based on RLZ 12 weeks exposure:
  - Sequence 1 Baseline (Visit 3) to Day 85 (Visit 15)
  - Sequence 2 Baseline (Visit 15) to Day 169 (Visit 27)
- Based on RLZ 24 weeks exposure:
  - Sequence 1 Baseline (Visit 3) to Day 169 (Visit 27)

Based on the above, participants in Sequence 1 will have 3 ADA classifications, and participants in Sequence 2 will have 2 ADA classifications. The combined ADA/NAb participant status will be derived only based on the ADA status for the entire study duration (ie, each participant will have only 1 ADA/NAb classification).

The ADA participant status is composed of 6 individual categories: ADA negative, inconclusive, and ADA positive whereby a positive participant's status is further subdivided into treatment-induced, treatment boosted, or non-treatment-emergent ADA positive.

However, the ADA participant status as defined in category 1 (ADA-NEG) can only be applied for participants having 2/3 (66.6%) of the protocol scheduled post-baseline ADA samples 'evaluable', (ie, neither missing as per schedule nor inconclusive) which is equivalent to the following:

- For the entire study duration
  - For Sequence 1, a minimum of 6/8 samples
  - For Sequence 2, a minimum of 4/5 samples
- RLZ 12 weeks
  - For Sequence 1, a minimum of 2/3 samples
  - For Sequence 2, a minimum of 2/3 samples
- RLZ 24 weeks
  - For Sequence 1, a minimum of 4/6 samples

Study participants that have a positive baseline value and no post-baseline values collected will be categorized as categories 2 (ADA-POS) and 5 (Non-TE-POS).

For a dropout participant, the participant status would be evaluated on the basis of the sample collection compared to all anticipated protocol scheduled samples assuming that they had actually completed the study.

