ⁱ Daily 24-hr pain and fatigue assessments to be collected every day for a week. Within the Screening Period, the daily average pain over the previous 24 hours will be captured using the Pain NRS through a diary over a 10-day period. Study participants require a minimum of 7 out of the 10 daily Pain NRS assessments over this 10-day period to be eligible for randomization.

^j The 24-hr pain and fatigue assessments to be collected for that day only.

^k To be performed before IMP dosing.

^l Study participants to provide their usual range doses of analgesics PRN.

^m On dosing days, PK, ADA, and IgG will be taken pre-dose.

ⁿ Total IgG only.

^o 80mL at Visit 3.

^p Samples for serum complement (C3, C4) and plasma complement (C3a, C5a) are collected predose at Visit 3 (Day 1) for all study participants. In study participants who experience an infusion reaction or hypersensitivity reaction at site, samples should also be taken 2 hours and 4 hours after the onset of the event, or otherwise as soon as possible but prior to the next dose.

^q 10mL at Visit 1 and Visit 3. In study participants who experience severe and/or serious headaches or suspected aseptic meningitis, exploratory biomarker samples should also be taken 4 hours after the onset of the event, or otherwise as soon as possible within 72 hours after the onset of the event.

Table 1-2: Schedule of Activities (Period 2 through End of Study)

Procedure	12-week Treatment Period: 2												Run-out	Run-out	EOT/EW	SFU/EOS
Visit number	15	16	17	18	19	20	21	22	23	24	25	26	27	28	-	-
Visit window	±2d	±2d	±2d	±2d	±2d	±2d	±2d	±2d	±2d	±2d	±2d	±2d	±2d	±2d	±7d	±7d
Week	13	14	15	16	17	18	19	20	21	22	23	24	25	26	28	32
Day	85	92	99	106	113	120	127	134	141	148	155	162	169	176	190	218
C-SSRS ^a	X												X		X	X
Urine pregnancy test	X				X				X				X		X	X
Laboratory assessments (full hematology, chemistry, urinalysis)	X				X				X				X		X	
Vital signs (blood pressure, pulse and temperature at every visit) ^b	X	X	X	X	X	X	X	X	X	X	X	X	X	X	X	X
Full physical examination ^c															X	X
Brief physical examination ^c	X												X			
Full neurological examination ^d															X	X
Pain NRS	X ^e	X ^e	X ^e	X ^e	X ^e	X ^e	X ^e	X ^e	X ^e	X ^e	X ^e	X ^f	X ^f	X ^e	X ^e	
BPI-SF	X				X				X				X		X	X
FIQR			X				X				X			X	X	X
Fatigue NRS	X ^e	X ^e	X ^e	X ^e	X ^e	X ^e	X ^e	X ^e	X ^e	X ^e	X ^f	X ^f	X ^f	X ^e	X ^e	
Pressure pain threshold ^g	X												X		X	X

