- Time course plot of mean CFB in BPI-SF Interference score, summarized by ADA participant categories 1, 6, 8, 9, 10, and 11, where the participant category is based on ADA/NAb data for the entire study duration. Separate plots for each treatment sequence will be generated.
  - For both Sequence 1 and Sequence 2, BPI-SF Interference scores from Visits 7, 11, 15, 19, 23 and 27 will be presented, with the x-axis presented in weeks.
- Spaghetti plots of percentage CFB for total IgG, for each of the ADA participant categories 1, 6, 8, and 9 (where the participant category is based on ADA/NAb data for the entire study duration). Individual samples that tested positive for ADA will be indicated on the plot. Separate plots for each treatment sequence will be generated.
  - For both Sequence 1 and Sequence 2, BPI-SF Interference scores from Visits 7, 11, 15, 19, 23 and 27 will be presented, with the x-axis presented in weeks.
- Scatterplot of individual change from Baseline in BPI-SF Interference score categorized by ADA titer tertile (including category ADA not present) for each scheduled assessment. The same plot will be repeated for NAb titer. Positive ADA/NAb samples that do not have an associated titer, will not be included in the plot.
  - For Sequence 1, ADA/NAb and BPI-SF data for Visits 11, 15, 23, and 27 will be displayed.
  - For Sequence 2, ADA/NAb and BPI-SF data for Visits 23 and 27 will be displayed. These visits will be overlaid with Visits 11 and 15 for Sequence 1, to reflect 12 weeks of exposure.
- Scatterplot of individual percentage change from Baseline for total IgG categorized by ADA titer tertile (including category ADA not present) for each scheduled assessment. The same

plot will be repeated for NAb titer. Positive ADA/NAb samples that do not have an associated titer, will not be included in the plot.

- For Sequence 1, ADA/NAb and BPI-SF data for Visits 4, 11, 15, 16, 23, and 27 will be displayed.
- For Sequence 2, ADA/NAb and BPI-SF data for Visits 16, 24, and 27 will be displayed. These visits will be overlaid with Visits 4, 11, and 15 for Sequence 1, to reflect 12 weeks of exposure.

Listings:

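### The 24-week ADA-negative rule for Sequence 1 counts samples without regard to when they were taken, and a baseline-positive participant with no post-baseline sample is labelled non-treatment-emergent

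*SAP*

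**What the plan says.** SAP 5.7 derives ADA participant status for three windows: the entire study, 12 weeks on rozanolixizumab and, for Sequence 1 only, 24 weeks ("Sequence 1 Baseline (Visit 3) to Day 169 (Visit 27"). Category 1, ADA-NEG, is open only to "participants having 2/3 (66.6%) of the protocol scheduled post-baseline ADA samples" evaluable. The SAP turns this into "For Sequence 1, a minimum of 4/6 samples" for 24 weeks and "For Sequence 1, a minimum of 6/8 samples" for the entire study. Table 5-7 adds that every post-baseline result must be negative. Neither place says when in the window the evaluable samples must fall. For dropouts, "the participant status would be evaluated on the basis of the sample collection compared to all anticipated protocol scheduled samples", so the denominator does not shrink when someone leaves.

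A separate sentence covers positive baselines: "Study participants that have a positive baseline value and no post-baseline values collected will be categorized as categories 2 (ADA-POS) and 5 (Non-TE-POS"). Table 5-7 defines category 5 by post-baseline results that are all negative or show no titre rise beyond assay variation. It reserves category 6, Inconclusive, for participants whose status cannot be determined because samples are missing or inconclusive. The first limb of category 6 covers a baseline-negative participant with too few evaluable samples.

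**The concern.** A label of ADA negative for 24 weeks of exposure should rest on some testing late in those 24 weeks. The retained denominator looks designed to stop early leavers from being called negative, but the Sequence 1 schedule is front-loaded: four of the six samples fall by Day 92, two of them a week apart. The count can therefore be met by someone who left soon after Treatment Period 2 began.

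The category 5 sentence raises a related question. Two participants with no post-baseline sample get different kinds of label according to their baseline: the negative one is Inconclusive, the positive one is placed in a category defined by post-baseline findings that do not exist.

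At stake is whether the ADA-NEG and Non-TE-POS counts mean what their names say.

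**Working it through.** **1. Reproducing the stated minima.** Minimum = 2/3 × n rounded up, with n the scheduled post-baseline ADA samples in the window.

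- Entire study, Sequence 1: n = 8, 5.33 → 6. Sequence 2: n = 5, 3.33 → 4.
- RLZ 12 weeks, either sequence: n = 3, 2.
- RLZ 24 weeks, Sequence 1: n = 6, 4.

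All five match SAP 5.7.

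**2. Which six samples.** The SAP 5.7 figure specification lists them: "For Sequence 1, ADA/NAb and BPI-SF data for Visits 4, 11, 15, 16, 23, and 27 will be displayed". Nominal days from Protocol Tables 1-1 and 1-2 are 8, 57, 85, 92, 141 and 169.

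**3. The earliest way to qualify.** Visits 4, 11, 15 and 16 give 4/6 = 66.7%. The last is on Day 92, and 169 − 92 = 77 days remain. Qualifying patterns number 15 + 6 + 1 = 22 (any four, five or six of six). Those without Visit 27 number 5 + 1 = 6, and one of these ends at Day 92.

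**4. The same participant over the entire study.** With only those four samples, 4/8 is below 6/8, so the status is Inconclusive.

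**5. Size.** Inputs: 20 in Sequence 1 (SAP 1.2); 25% dropout with uniform timing (SAP 3). Assumption: uniform means over the 168 treatment days, since the SAP gives no interval.

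- Expected dropouts: 20 × 0.25 = 5.
- Leaving between Visit 16 and Visit 23: 5 × (141 − 92)/168 = 1.46, or 1.46/20 = 7.3% of the sequence.

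This is an upper figure: it needs all earlier samples negative and no early-withdrawal (EW) sample counted.

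**6. Where the 24-week label is used.**

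- Category table for the 24-week window: affected, in the ADA-NEG and Inconclusive counts.
- IgG by ADA category, 24 weeks: affected. It takes the maximum change in Treatment Period 2, so a leaver's early Period 2 IgG values enter under ADA-NEG.
- BPI-SF by ADA category, 24 weeks: it uses Visit 27, and a leaver has no Visit 27 score.
- TEAE-by-ADA tables and combined ADA/NAb status: these use the entire-study classification (step 4), so they are not affected.
- TE-POS percentage: the denominator is everyone with a category, Inconclusive included, so it does not move.

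**7. The category 5 sentence.** With no post-baseline sample, the category 5 definition is met only vacuously, because a boost was never tested. To land there a participant must be positive at baseline and leave before the first on-drug sample (Days 1 to 8 in Sequence 1, Days 85 to 92 in Sequence 2), with no EW or follow-up sample. On the same dropout model that is 5 × 7/168 = 0.2 per active sequence, multiplied by the prevalence of pre-existing ADA, which the documents do not give. The TEAE-by-ADA tables display category 5 on the entire-study classification, so this label does reach them.

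**The case against.** The strongest reply is that little follows from the rule.

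- **Reach.** A reader might infer that the adverse-event and efficacy comparisons by ADA status are contaminated, or that treatment-emergent ADA is understated as a percentage. For the Day 92 participant the documents do not support either, for the reasons in step 6. This part of the objection stands.
- **Untested participants.** A reader might also infer that untested people are called ADA negative. The Day 92 participant has four evaluable negatives over 13 weeks and is untested only afterwards. Only the baseline-positive participant with no post-baseline sample is literally untested, and that person still counts as ADA-POS (category 2) under an explicit, pre-specified rule.
- **EW sample.** Protocol 8.6 asks for an ADA sample at the EW visit, and SAP 5.7 assigns sample status at unscheduled visits too, so a leaver should be tested on departure. That lowers the 1.5. It does not close the gap, because SAP 5.1.5 omits ADA from the assessments re-mapped from EW, so whether the sample belongs to the 24-week window is undefined.
- **The 12-week rule.** Two of three samples can also be met without the last one. There the shortfall is one sample and 28 days (85 − 57, or 169 − 141), and the point is not pressed that far.
- **Visibility.** ADA is exploratory, and the by-visit tables and listings show missing samples. That limits the harm but does not make the participant-level label correct.

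**Conclusion.** Two stated rules give labels that the data behind them do not support, and the consequence is small. For the 24-week window, at most about 1.5 of 20 Sequence 1 participants could be ADA-NEG with no scheduled sample after Day 92. This assumes 25% dropout spread uniformly over 168 days, negative earlier samples and no counted EW sample. It changes the 24-week ADA-NEG and Inconclusive counts and the 24-week IgG-by-ADA summary, and nothing else identified here. The same four samples give Inconclusive for the entire study, so the two rules diverge on one person.

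The Non-TE-POS assignment is rarer, well under one participant on the same model, but it does reach the TEAE-by-ADA tables. Neither point bears on the primary or secondary efficacy analyses. This is a low-cost improvement to SAP 5.7.

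**What to change.** In SAP 5.7:

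1. For RLZ 24 weeks, keep 4/6 and add that at least one evaluable sample must be at the end of the window or later: Visit 27, or a later EOT or SFU sample if Visit 27 is missing. Otherwise the status is Inconclusive. Raising the count alone does not work: 5/6 can still end at Day 141, and only 6/6 forces Day 169.
2. State how an EW ADA sample counts: whether it contributes to the 4/6, and whether it can meet the end-of-window condition for someone who stopped early.
3. Classify a baseline-positive participant with no evaluable post-baseline sample as ADA-POS (category 2) and Inconclusive for treatment-emergent status, not category 5. Category 6 needs a further limb for this: its first limb requires a negative baseline, and its second requires that no other category is met.

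The cost is SAP wording and derivation code, with no change to data collection. The downside is that a few participants move from ADA-NEG or Non-TE-POS to Inconclusive. Of the 22 patterns that now qualify, 16 contain Visit 27 and are untouched. Someone with five negatives who leaves after Day 141 would also move if no later sample exists: 5 × (169 − 141)/168 = 0.83 expected, so at most about 1.46 + 0.83 = 2.3 of 20 in Sequence 1.

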**Table 5-7: ADA Participant Status Categories**

Term	Definition	Category
ADA participant status categories		
ADA-NEG (Pre ADA negative – treatment induced ADA negative)	Study participants who have negative ADA sample status at baseline and at all sampling time points post-baseline with the number of evaluable samples (non- missing per schedule nor inconclusive) more or equal to 2/3 as defined above.  [Note: study participants with baseline samples missing and negative ADA status at all sampling time post-baseline are included in this category; based on the following rationale: in case the participant would be pre-Ab positive, the participant is expected to present ADA positive samples post-baseline]	1
ADA-POS	Study participants who have a positive ADA sample status at any time point (either Baseline, or post-Baseline)	2

Term	Definition	Category
TI-POS (Pre ADA negative – Treatment Induced ADA positive)	Study participants who have a negative ADA status at baseline and positive ADA status at any sampling point post-Baseline.	3
TB-POS (Pre ADA positive – Treatment Boosted ADA positive)	Study participants who have a positive ADA status at baseline and positive ADA status at any sampling point post-baseline with non-missing increased titer values compared to baseline (>fold difference from Baseline value as determined by the MSR of the assay).	4
Non-TE-POS (Pre-ADA positive- Non-Treatment - Emergent ADA positive)	Study participants who have a positive ADA status at baseline and 1) negative ADA status at all evaluable sampling points post-baseline or 2) positive ADA status at any evaluable sampling points post- baseline with non-missing titer values of the same or lower magnitude as baseline ( $\leq$ fold difference from Baseline value as determined by the MSR of the assay).	5
Inconclusive	Study participant for who the ADA participant status cannot be defined due to missing or inconclusive samples. Inconclusive [1]: Study participant that had negative ADA status at baseline and post-baseline samples missing per schedule or inconclusive that is higher than the % allowed as defined above, while others post-baseline samples are ADA negative up to the time point of interest. Inconclusive [2]: Participants who do not satisfy any of the above criteria.	6
Combined ADA participant status categories		
TE-POS (TE ADA positive)	Includes study participants defined in category 3 and 4	7
Treatment emergent ADA positive – NAb positive (TE-POS, NAb-POS)	Study participants in category 7 who have at least one NAb positive sample	8
Treatment emergent ADA positive – NAb negative (TE-POS, NAb-NEG)	Study participants in category 7 who have no NAb positive samples	9
Non-treatment emergent ADA positive – NAb positive (Non-TE-POS, NAb-POS)	Study participants in category 5 who have at least one NAb positive sample	10
Non-treatment emergent ADA positive – NAb negative (Non-TE-POS, NAb-NEG)	Study participants in category 5 who have no NAb positive samples	11

The fold difference increase from baseline value, ie, the minimum significant ratio (MSR) determined during assay validation, will be reported in the relevant tables, listings and figures. It reflects the fold difference in titer level that considered higher than the assay variation in titer determination.

Calculation of Fold Increase for use of MSR, and for classifying ‘Non-TE-POS (Pre-ADA positive- Non-Treatment-Emergent ADA positive)’ and ‘TB-POS (Pre ADA positive – Treatment Boosted ADA positive)’ category:

Fold increase= post-dose titer/baseline titer

The following summaries, figures and listings will be produced and will be presented using the SS-r:

Tables:

- Summary table displaying the number and percentage of study participants with a positive ADA, negative ADA, inconclusive or missing ADA sample status at the time of each visit by planned treatment sequence.
- Summary table displaying the number and percentage of study participants with a positive NAb, negative NAb, inconclusive or missing NAb sample status at the time of each visit by planned treatment sequence.
- Number and percentage of study participants in each of the individual and combined ADA participant status categories and combined categories (1-11) presented in [Table 5-7](#) for each time period specified above. The denominator will be the total number of study participants with an individual ADA participant category defined for each time period.
- Total prevalence of pre-existing ADA and NAb, defined as number and percentage of participants having an ADA/NAb positive sample status at baseline, with the denominator being the total number of study participants having an evaluable ADA/NAb sample result at baseline.
- The first occurrence of treatment-emergent ADA positivity: cumulative number and percentage of TE-ADA positive participants (category 7) who are ADA positive for the first time based on samples collected over the entire study duration, including SFU.
- Summary table of mean maximum percentage change from Baseline in total IgG summarized by ADA participant categories (1-6) for the following:
  - Sequence 1, Treatment Period 1 (RLZ 12 weeks) using ADA participant category based on RLZ 12 weeks exposure and maximum percent change from Baseline in total IgG in Treatment Period 1.
  - Sequence 2, Treatment Period 2 (RLZ 12 weeks) using ADA participant category based on RLZ 12 weeks exposure and maximum percent change from Baseline in total IgG in Treatment Period 2.
  - Sequence 1, Treatment Period 1 and Treatment Period 2 (RLZ 24 weeks) using ADA participant category based on RLZ 24 weeks exposure and maximum percent change from Baseline in total IgG in Treatment Period 2

- Sequence 1 Treatment Period 1 and Sequence 2, Treatment Period 2 (RLZ 12 weeks) using ADA participant category based on RLZ 12 weeks exposure and maximum percent change from Baseline in total IgG in Treatment Period 1 for Sequence 1, and Treatment Period 2 for Sequence 2.
- Summary table of mean change from Baseline in BPI-SF Interference score in Treatment Periods 1 and 2, summarized by ADA participant categories (1-6) for the following:
  - Sequence 1, Treatment Period 1 (RLZ 12 weeks) using ADA participant category based on RLZ 12 weeks exposure and change from Baseline in BPI-SF interference score at Visit 15.
  - Sequence 2, Treatment Period 2 (RLZ 12 weeks) using ADA participant category based on RLZ 12 weeks exposure and change from Baseline in BPI-SF interference score at Visit 27.
  - Sequence 1, Treatment Period 1 and Treatment Period 2 (RLZ 24 weeks) using ADA participant category based on RLZ 24 weeks exposure and change from Baseline in BPI-SF interference score at Visit 27.
  - Sequence 1 Treatment Period 1 and Sequence 2, Treatment Period 2 (RLZ 12 weeks) using ADA participant category based on RLZ 12 weeks exposure and change from Baseline in BPI-SF interference score at Visit 15 for Sequence 1, and Visit 27 for Sequence 2.
- Overall summary table of TEAEs summarized by ADA participant categories 1, 5, 6, and 7 where the participant category is based on ADA data for the entire study duration. This table will include the following:
  - Sequence 1 – all TEAEs occurring on or after the first dose in Treatment Period 1, up to the SFU Visit.
  - Sequence 2 – all TEAEs occurring on or after the first dose in Treatment Period 2, up to the SFU Visit.
- Summary table of incidence of TEAE by ADA participant category 1, 5, 6, and 7 for the where the participant category is based on ADA data for the entire study duration, as described for the overall summary table. This table will be repeated for the AEOF hypersensitivity reactions, anaphylactic reactions and injection site reactions (defined as AEOF in [Section 13.7](#)).

Figures:

- Individual time course plots for ADA positive study participants, (within categories 3,4 and 5) representing ADA and NAb titers (on log-scale), percentage change from Baseline for total IgG and change from Baseline for BPI-SF Interference Score. This will include the following:
  - For Sequence 1: All data from Visit 3 (ADA Baseline) to SFU, with the x-axis presented in weeks
  - For Sequence 2: All data from Visit 15 (ADA Baseline) to SFU, with the x-axis presented in weeks

- A plot of the median change from Baseline in Total IgG over time by cumulative ADA positivity status and planned treatment sequence. The ADA positive status will be considered in a cumulative manner at each time point (ie, if a participant has had at least one positive sample at any time point up to and including the given time point, that participant will be counted as positive at that time point, regardless of any subsequent negative measurements. In addition, if the Baseline sample is missing then the sample will be classified as being negative for the cumulative ADA status). This plot will include the following:
  - For Sequence 1: All data from Visit 3 (ADA Baseline) to SFU, with the x-axis presented in weeks
  - For Sequence 2: All data from Visit 15 (ADA Baseline) to SFU, with the x-axis presented in weeks
- A plot of median percent change from Baseline in Total IgG over time by cumulative ADA positivity status and planned treatment sequence, as described above.
- A box-and-whisker plot of maximum post-Baseline ADA titer (on log-scale) versus ADA participant category (where the participant category is based on ADA/NAb data for the entire study duration) for categories 8, 9, 10, and 11 by treatment sequence. The same plot will be repeated for NAb titer for ADA participant categories 8 and 10.
- Time course plot of mean CFB in BPI-SF Interference score, summarized by ADA participant categories 1, 6, 8, 9, 10, and 11, where the participant category is based on ADA/NAb data for the entire study duration. Separate plots for each treatment sequence will be generated.
  - For both Sequence 1 and Sequence 2, BPI-SF Interference scores from Visits 7, 11, 15, 19, 23 and 27 will be presented, with the x-axis presented in weeks.
- Spaghetti plots of percentage CFB for total IgG, for each of the ADA participant categories 1, 6, 8, and 9 (where the participant category is based on ADA/NAb data for the entire study duration). Individual samples that tested positive for ADA will be indicated on the plot. Separate plots for each treatment sequence will be generated.
  - For both Sequence 1 and Sequence 2, BPI-SF Interference scores from Visits 7, 11, 15, 19, 23 and 27 will be presented, with the x-axis presented in weeks.
- Scatterplot of individual change from Baseline in BPI-SF Interference score categorized by ADA titer tertile (including category ADA not present) for each scheduled assessment. The same plot will be repeated for NAb titer. Positive ADA/NAb samples that do not have an associated titer, will not be included in the plot.
  - For Sequence 1, ADA/NAb and BPI-SF data for Visits 11, 15, 23, and 27 will be displayed.
  - For Sequence 2, ADA/NAb and BPI-SF data for Visits 23 and 27 will be displayed. These visits will be overlaid with Visits 11 and 15 for Sequence 1, to reflect 12 weeks of exposure.
- Scatterplot of individual percentage change from Baseline for total IgG categorized by ADA titer tertile (including category ADA not present) for each scheduled assessment. The same

plot will be repeated for NAb titer. Positive ADA/NAb samples that do not have an associated titer, will not be included in the plot.

- For Sequence 1, ADA/NAb and BPI-SF data for Visits 4, 11, 15, 16, 23, and 27 will be displayed.
- For Sequence 2, ADA/NAb and BPI-SF data for Visits 16, 24, and 27 will be displayed. These visits will be overlaid with Visits 4, 11, and 15 for Sequence 1, to reflect 12 weeks of exposure.

Listings:

- A listing of the by visit ADA/NAb results including the results from the screening assay, confirmatory assay, and titration assay (titer level), the fold change compared to baseline and the ADA/NAb sample status will be presented by planned treatment sequence and participant. This listing will also contain the time since the previous administration of IMP (in days).
- A listing of the ADA and ADA/Nab participant categories will be presented by planned treatment sequence.
  - Participants randomized to Sequence 1 will have 3 ADA classifications (based on ADA data for the entire study duration, 12 weeks and 24 weeks), and 1 ADA/NAb classification (based on ADA/NAb data for the entire study duration)
  - Participants randomized to Sequence 2 will have 2 ADA classifications (based on ADA data for the entire study duration, and 12 weeks) and 1 ADA/Nab classification (based on ADA/NAb data for the entire study duration).
- A listing of the by visit ADA and NAb sample status, ADA titer, NAb titer, rozanolixizumab plasma concentration, percentage change from Baseline for total IgG and IgG subclasses, and change from Baseline for BPI-SF Interference score will be presented.
- A listing of the following TEAEs will be generated:
  - For participants randomized to Sequence 1 – all TEAEs occurring on or after the first dose in Treatment Period 1, up to the SFU Visit.
  - For participants randomized to Sequence 2 – all TEAEs occurring on or after the first dose in Treatment Period 2, up to the SFU Visit.

This listing will include the ADA and NAb sample status and ADA and NAb titers at the closest sampling time point to the date of onset of the TEAE (this could be prior to or after the date of onset). If both sampling points are equidistant to the TEAE, then the prior one is selected.

